8.2 Data collection

Designated unblinded Investigator staff will enter the data required by the protocol into the eCRF system. Designated Investigator study center staff will not be given access to the system until they have been trained.

The blinded assessor for the PASI and IGA mod 2011 assessment will report data in a separate database. The blinded assessor must not have access to details that could compromise the blinding.

Automatic validation procedures within the system check for data discrepancies during and after data entry and, by generating appropriate error messages, allow the data to be confirmed or corrected online by the designated Investigator study center staff. The Investigator must certify that the data entered into the eCRFs are complete and accurate. After database lock, the Investigator will receive copies of the patient data for archiving at the investigational study center.

8.3 **Database management and quality control**

Novartis staff or designated CRO staff review the data entered into the eCRFs by Investigator/qualified study center staff for completeness and accuracy and instruct the Investigator/qualified study center staff to make any required corrections or additions. Queries are sent to the investigational study center using an electronic data query. Investigator/qualified study center staff is required to respond to the query and confirm or correct the data. If the electronic query system is not used, a paper Data Query Form will be faxed to the study center. Investigator/qualified study center staff will complete and sign the faxed copy and fax it back to Novartis staff that will make the correction to the database. The signed copy of the Data Query Form is kept at the study center.

Concomitant medications entered into the database will be coded using the World Health Organization Drug Reference List, which employs the Anatomical Therapeutic Chemical classification system. Concomitant procedures, non-drug therapies and AEs will be coded using the Medical dictionary for regulatory activities (MedDRA) terminology.

Laboratory samples will be processed centrally and the results will be sent electronically to Novartis (or a designated CRO). All ECGs will be independently reviewed by a central reader. Instructions for the collection and transmission of the ECGs to the independent reviewer will be provided in the ECG Investigator manual.

The blinded assessors for PASI and IGA mod 2011 assessments will use electronic devices to report PASI and IGA mod 2011 data. These data will be collected centrally and the results

will be sent electronically to Novartis (or a designated CRO). In case electronic devices cannot be used a paper-based process is acceptable and details of the whole process are described in a separate user manual.

Randomization codes, data about all study drug dispensed to the patient and some efficacy data will be tracked using IRT. The system will be supplied by Novartis staff or a vendor that will also manage the database. The database will be sent electronically to Novartis (or a designated CRO). Details are provided in a user manual.

8.4 **Data Monitoring Committee**

In alignment with the EMA Guideline on Data Monitoring Committees (DMCs) (EMEA/CHMP/EWP/5872/03 Corr) no DMC is deemed to be required for this Phase 3b clinical study. A pharmacovigilance review concluded that substantial amount of safety data for the study drugs have been collected through all study phases and that a DMC would not be beneficial for the study. Furthermore, the study population is not considered to have an elevated risk of more severe outcomes during this study, which is also in accordance with US, Department of Health and Human Services FDA guidelines (Guidance for Clinical Trial Sponsors. Establishment and Operation of Clinical Trial Data Monitoring Committees, 2006).

8.5 **Adjudication Committee**

Not applicable.

9 Data analysis

For the analysis of Treatment Period 1 (until/including Week 24) all patients will receive the same treatment:

• secukinumab 300 mg s.c. every 4 weeks

For the analysis of Treatment Period 2 (maintenance period Week 24 to Week 52) the following treatment groups are utilized.

Only patients with at least a 90% reduction in PASI score from Baseline will be randomized at Week 24 on a 1:1 basis to either Group 1 or Group 2:

- Group 1 (recommended maintenance treatment): secukinumab 300 mg s.c. every 4 weeks.
- Group 2 (experimental maintenance treatment): secukinumab 300 mg s.c. every 6 weeks.

Patients who did not achieve a PASI 90 at Week 24 but achieved at least a PASI 75 response are eligible for dose frequency intensification and will be randomized to either Group 3 or Group 4:

- Group 3 (recommended maintenance treatment): secukinumab s.c. 300 mg every 4 weeks.
- Group 4 (experimental maintenance treatment): secukinumab s.c. 300 mg every 2 weeks.

Patients with less than a 75% reduction in PASI score from Baseline at Week 24 are not eligible for randomization and will be discontinued from the study.

Novartis

Summary statistics for continuous variables will include N, mean, standard deviation, minimum, median, maximum. Summary statistics for discrete variables will be presented in contingency tables and will include absolute and relative frequencies.

If not otherwise specified, p-values will be presented as two-sided p-values and two-sided CIs will be displayed.

9.1 Analysis sets

The **Safety Set for Treatment Period 1 (SAF-TP1)** will include all patients who received at least one dose of study drug during this treatment period.

The Safety Set for Maintenance Treatment Period 2 (SAF-TP2) will include all patients who were randomized and received at least one dose of study drug at- or after the Week 24 visit. For safety evaluations, the patient groups of PASI 90 responders and PASI 75 responders who do not achieve a PASI 90 response will be pooled; therefore, only 3 dosing groups will be compared:

- secukinumab 300 mg s.c. every 2 weeks (patients from Group 4)
- secukinumab 300 mg s.c. every 4 weeks (patients from Group 1 pooled with Group 3)
- secukinumab 300 mg s.c. every 6 weeks (patients from Group 2)

Patients will be analyzed according to the treatment they received.

The Full Analysis Set for Treatment Period 2 of PASI 90 Responders (FAS-P90R) will include all patients who are rated as PASI 90 responders at the Week 24 visit, were randomized to treatment groups 1 or 2 and who received at least one dose of study drug at- or after visit Week 24.

The Full Analysis Set for Treatment Period 2 of PASI 75 Responders who do not achieve a PASI 90 Response (FAS-P75P) will include all patients who are rated as PASI 75 responders who do not achieve a PASI 90 response at visit Week 24, were randomized to treatment Group 3 or 4 and who received at least one dose of study drug at- or after visit Week 24.

The Per-Protocol Set for Treatment Period 2 of PASI 90 Responders (PP-P90R) will include all patients from the FAS-P90R who complete the study as scheduled without any major deviations from the protocol which may affect the primary outcome of this study. Such deviation will be defined in the Data Validation Plan or similar document and in the protocol of the blind data review without knowledge of the treatment group assignment.

Efficacy evaluations will be performed according to the treatment assigned at randomization.

9.2 Patient demographics and other baseline characteristics

Summary statistics will be presented for continuous demographic and Baseline characteristics. The number and percentage of patients in each category will be presented for categorical variables. Separate tables will be produced for all patients treated (SAF-TP1, totals only) and

for patients randomized into the maintenance period (FAS-P90R and FAS-P75P, each by treatment group).

9.2.1 **Medical history**

Any condition entered as medical history or current medical conditions at Baseline (including cardiovascular risk factors) will be coded using the MedDRA dictionary. They will be summarized by MedDRA system organ class (SOC) and preferred term of the MedDRA. Summaries for psoriasis specific medical history will also be provided.

9.3 **Treatments**

The duration of exposure to study drug will be summarized for all patients treated (SAF-TP1, totals only) and for patients randomized into the maintenance period (FAS-P90R and FAS-P75P, each by treatment group). Compliance will be calculated in percent as the number of injections administered divided by the number of injections scheduled according to the protocol.

9.3.1 Prior and concomitant treatment

Prior and concomitant medications will be summarized by treatment group in separate tables.

Prior medications are defined as treatments taken and stopped prior to first dose of study drug. Any medication given at least once between the day of first dose of study drug and the last day of study will be a concomitant medication, including those which were started pre-Baseline and continued into the treatment period.

Medications will be presented in alphabetical order, by anatomical therapeutic classification (ATC) codes and grouped by anatomical main group. Tables will also show the overall number and percentage of patients receiving at least one treatment of a particular ATC code and at least one treatment in a particular anatomical main group.

In addition, significant prior and concomitant non-drug therapies and procedures will be summarized by primary SOC and MedDRA preferred term.

9.4 Analysis of the primary variable

9.4.1 Variable

The primary variable is the maintenance of the PASI 90 response rate at Week 52 in the FAS-P90R, which is the proportion of patients who maintain their PASI 90 response assessed at Week 24 also at Week 52. The aim of the primary analysis of this study will be to demonstrate the non-inferiority of the 6-weekly dosing group compared to the 4-weekly dosing group with respect to the primary endpoint in the FAS-P90R.

Statistical model, hypothesis, and method of analysis 9.4.2

The statistical null-hypothesis to be rejected is that the odds ratio of maintaining a PASI 90 response for patients 4-weekly dosing versus patients on 6-weekly dosing exceeds the non-inferiority margin of $1+\delta$.

Let π_j denote the probability of a PASI 90 response at Week 52 for treatment group j, j=0, 1 where

- 0 corresponds to 4-weekly dosing
- 1 corresponds to 6-weekly dosing

The following hypothesis will be tested

$$H_{0.1}$$
: $(\pi_0 / [1 - \pi_0]) / (\pi_1 / [1 - \pi_1]) \ge 1 + \delta \text{ versus } H_{A1}$: $(\pi_0 / [1 - \pi_0]) / (\pi_1 / [1 - \pi_1]) < 1 + \delta$

The **primary analysis** will be performed comparing dosing groups (Group 1 vs Group 2) with respect to the primary efficacy variable in a logistic regression model with the factors treatment, country, body weight ($< 90 \text{ kg} \text{ or } \ge 90 \text{ kg}$), and PASI 90 response (Y/N) at Week 16. The odds ratio with its corresponding 95% CI will be given (please notice that the upper limit of a 2-sided 95% CI is identical to the upper limit of a one-sided 97.5% CI, which would correspond to a one-sided test with significance level 2.5%). Additionally, a (one-sided) p-value for the shifted null-hypothesis will be computed.

9.4.3 Choice of the non-inferiority margin

Non-inferiority is defined as a difference in PASI 90 maintenance rate between 4- and 6-weekly dosing not exceeding 15% on a rate difference scale. Data from a pooled CAIN457A database (CAIN4572302 and CAIN4572303) suggest that the PASI 90 maintenance rate at Week 52 under 4-weekly dosing might be 81.8%. However, since the logistic regression model used for the primary analysis provides estimates on the odds-ratio scale, the numbers above have to be translated into this scale. Inserting these numbers into the respective formulas results in a non-inferiority-margin on the odds-ratio-scale of $1+\delta=2.23$. Non-inferiority of 6-weekly vs 4-weekly dosing will be claimed, if the upper limit of the CI for the odds ratio does not exceed 2.23.

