#### 1.8.2 Statistical hypothesis, model, and method of analysis

The statistical null-hypothesis to be rejected in the primary analysis is that the odds ratio of maintaining a PASI 90 response for patients with secukinumab 4-weekly dosing versus patients on secukinumab 6-weekly dosing exceeds the non-inferiority margin of  $1+\delta$ .

The primary hypothesis is stated as follows:

Let  $\pi_j$  denote the probability of a PASI 90 response at Week 52 for dosing group j, j=0, 1, where

- 0 corresponds to 4-weekly dosing
- 1 corresponds to 6-weekly dosing

The following hypothesis will be tested

$$H_{01}$$
:  $(\pi_0 / (1 - \pi_0)) / (\pi_1 / (1 - \pi_1)) \ge 1 + \delta$  versus  $H_{A1}$ :  $(\pi_0 / (1 - \pi_0)) / (\pi_1 / (1 - \pi_1)) < 1 + \delta$ 

The non-inferiority margin  $1+\delta$  is calculated as 2.23 assuming a PASI 90 response maintenance rate of 81.8% under 4-weekly dosing treatment scheme and using a 15% non-inferiority margin. The **primary analyses** will be performed comparing dosing groups (Group 1 vs. Group 2) with respect to the primary efficacy variable in a logistic regression model with the factors dosing group, country, PASI 90 response at Week 16 (Yes, No) and body weight at Week 24 (< 90 kg or  $\geq$  90 kg, for model definition see Section 2.2.2). The odds ratios and their two-sided 95%-Wald confidence intervals (CIs) will be given.

In case of subgroup analyses where the grouping variable is one of the above described factors in the logistic regression model the respective factor is excluded from the model.

Additionally, the one-sided p-value for the shifted null-hypothesis will be given. The respective test statistic is calculated as

$$\frac{\hat{\beta}-\beta_0}{se_{\hat{\beta}}}$$

where  $\hat{\beta}$  is the type 3 maximum likelihood estimate of the dosing group parameter in the logistic regression model and  $se_{\hat{\beta}}$  is its standard error.  $\beta_0$  is the non-inferiority margin of the estimator which corresponds to the  $\delta$  from the above null-hypothesis and is therefore set to  $ln(1+\delta) = ln(2.23) = 0.80$ .

Only in case that the number of patients with response (or non-response) in one of the groups is 5 or lower, exact logistic regression will be used for the primary analysis instead of logistic regression using maximum-likelihood based estimators.

The primary analysis set will be the FAS-P90R.

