### 1.8.6 Testing strategy of the primary and the key secondary analysis

**Significance Level:** The primary analysis will be performed at the one-sided 2.5% level which corresponds to a two sided 5% level. Non-inferiority of 6-weekly vs. 4-weekly dosing will be claimed, if the upper limit of the two sided 95%-Wald CI for the odds ratio estimated in the above described logistic regression model does not exceed 2.23. The key secondary analysis will be performed on the two-sided 5% level of significance. The test decision will be based on the Wald test, i.e. if the p-value from the test is below 0.05.

**Multiplicity issues:** The key secondary analysis will be included in the confirmatory testing strategy using a hierarchical testing strategy. The key secondary hypothesis will be a priori ordered below the primary hypothesis. This means that no multiplicity adjustment of the significance level is required; however, confirmatory evidence will be claimed only if non-inferiority with regard to the primary endpoint has been successfully demonstrated before. Otherwise, the result for the secondary endpoint will be interpreted as being purely explorative, independent of the nominal p-value.

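### Non-inferiority is defined and powered as a 15-point rate difference but decided by a fixed odds ratio of 2.23, so the effective margin moves with the 4-weekly rate and power at the planned rates is about 75%, not 90%

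*Protocol*

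**What the plan says.** Protocol 9.4.3 sets the definition in percentage points: "Non-inferiority is defined as a difference in PASI 90 maintenance rate between 4- and 6-weekly dosing not exceeding 15% on a rate difference scale". Protocol 3.2 justifies the margin clinically in percentage points only. Protocol 9.4.3 then converts 15 points at a historical 4-weekly rate of 81.8% into an odds ratio, because the logistic model works on that scale, and allows the claim "if the upper limit of the CI for the odds ratio does not exceed 2.23".

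The SAP keeps the constant. Section 1.8.2 says the limit "is calculated as 2.23 assuming a PASI 90 response maintenance rate of 81.8% under 4-weekly dosing treatment scheme" and builds ln(2.23) = 0.80 into the test statistic. Section 1.8.6 gives the decision rule: "Non-inferiority of 6-weekly vs. 4-weekly dosing will be claimed, if the upper limit of the two sided 95%-Wald CI for the odds ratio" from the logistic model is no higher than 2.23. It adds: "The primary analysis will be performed at the one-sided 2.5% level which corresponds to a two sided 5% level". The model adjusts for country, body weight and PASI 90 response at Week 16.

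An unadjusted risk difference with a 95% interval is planned (Protocol 9.4.5; SAP 1.8.4), but only as a supportive analysis and with no 15-point criterion. The sample size (Protocol 9.7; SAP 1.11) is 554 per group for 90% power at one-sided 2.5%, with true rates of 81.8% and 74.8% and a 15-point margin, rounded up to 570.

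**The concern.** One odds ratio corresponds to a different rate difference at every control rate. The definition and the decision rule therefore coincide only near the assumed 81.8%, and nothing in the plan updates 2.23 if the 4-weekly arm behaves differently. The rule is looser than 15 points below that rate and stricter above it. Missing Week 52 assessments count as non-response, so more drop-out than in the historical studies would lower the 4-weekly rate and loosen the effective margin.

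The definition and the sample size use one scale and the decision another, so the stated 90% power does not belong to the test that will be run. The primary decision also gates the confirmatory status of the key secondary comparison (SAP 1.8.6), so a failure caused by the change of scale would cost both.

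**Working it through.** **Inputs from the documents.** Margin 15 points and 4-weekly rate 81.8% (Protocol 9.4.3). Limit 2.23 (Protocol 9.4.3; SAP 1.8.2, 1.8.6). True rates 81.8% and 74.8%, one-sided 2.5%, 90% power, 554 and 570 per group (Protocol 9.7).

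**Assumed here.** 4-weekly rates other than 81.8%, and the covariate illustration in step 5.

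**1. The limit reproduces.** (0.818/0.182) / (0.668/0.332) = 2.234, stated as 2.23.

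**2. The sample size reproduces on the rate-difference scale.** n = (1.960 + 1.282)² × (0.818×0.182 + 0.748×0.252) / (0.15 − 0.07)² = 553.9, so 554. Power is 90.0% with 554 and 90.8% with 570.

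**3. Effective margin.** For a 4-weekly rate p0, let o = [p0/(1 − p0)]/2.23. The 6-weekly rate at the limit is o/(1 + o), and the margin is p0 minus that rate.

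**4. Unadjusted chance of a claim at a true deficit of exactly 15 points, 570 per group.** With p1 = p0 − 0.15, the chance is Φ[(ln 2.23 − ln OR)/SE − 1.960], where SE² = [1/(p0(1 − p0)) + 1/(p1(1 − p1))]/570. At 75%, for example: OR 2.000, SE 0.1291, Φ(0.843 − 1.960) = 13.2%.

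| 4-weekly rate | 6-weekly rate at OR 2.23 | Effective margin (points) | OR at a 15-point deficit | Chance of a claim (nominal 2.5%) |
|---|---|---|---|---|
| 75% | 57.4% | 17.6 | 2.000 | 13.2% |
| 80% | 64.2% | 15.8 | 2.154 | 4.4% |
| 81.8% | 66.8% | 15.0 | 2.234 | 2.4% |
| 85% | 71.8% | 13.2 | 2.429 | 0.6% |
| 90% | 80.1% | 9.9 | 3.000 | near 0 |

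The maximum possible margin is (√2.23 − 1)/(√2.23 + 1) = 19.8 points, at a 4-weekly rate of 59.9%.

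**5. Effect of adjustment.** The limit comes from marginal rates but is compared with a conditional odds ratio, which lies further from 1. Suppose 85% are Week 16 responders and that covariate has an odds ratio of 4. For each arm, solve 0.85·expit(a + ln 4) + 0.15·expit(a) = rate; the conditional odds ratio is exp(a0 − a1). At a 15-point deficit it is 2.35 at 81.8%, 2.27 at 80% and 2.09 at 75%. The chances of a claim become 1.0%, 1.9% and 6.8%. At 81.8%, a limit of 2.23 then means 13.9 points. With a covariate odds ratio of 2, the chances at 80% and 75% are 3.7% and 11%.

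**6. Power of the rule actually used.** At 81.8% versus 74.8%, OR = 1.514 and ln OR = 0.4149. With 554 per group, SE = √[(6.717 + 5.305)/554] = 0.1473, so power = Φ[(0.8020 − 0.4149)/0.1473 − 1.960] = Φ(0.668) = 75%. With 570 per group it is 76%. About 843 per group would be needed for 90%. Adjustment does not recover this: in the step 5 illustration the conditional odds ratio is 1.555 with SE 0.150 at 570 per group, giving Φ[(0.8020 − 0.4414)/0.150 − 1.960] = 67%.

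**The case against.** The hypotheses are written on the odds-ratio scale, the conversion is disclosed and pre-specified, and the test controls 2.5% against that stated null. A fixed odds-ratio margin is an accepted choice. The risk difference will be reported, so a reader could see a conflict. The 81.8% comes from pooled trials of the same 4-weekly regimen in biologic-naïve patients, with the same handling of drop-outs. All of this is fair, and it makes the problem one of coherence rather than concealment or faulty arithmetic. It does not cure a rule that departs from the plan's own definition and sample-size basis. The plan also does not say how to read a result where the two scales disagree.

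A reader might go further and infer that deficits of about 20 points will pass. The documents do not support that. The 19.8-point ceiling needs a 4-weekly rate near 60%, some 22 points below the planning figure. It is also a true deficit at the boundary, where a claim still has only about a 2.5% chance. With 570 per group, unadjusted, the largest observed deficit that passes is 9.0 points at 81.8%, 11.6 at 75% and 14.0 at 60%. At an observed 80%, a result that just passes has a rate-difference upper limit of 14.8 points, so disagreement in the loose direction starts only a little below 80%.

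A reader might also take the 4.4% and 13% as the error rates of the planned analysis. They are unadjusted, and the planned model lowers them by an amount that the documents do not let one fix.

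**Conclusion.** The mismatch is real. Its firmest consequence rests on the plan's own figures: at 81.8% versus 74.8%, the decision rule has about 75% unadjusted power with 554 per group (76% with 570), while the plan states 90%. The drift in the margin depends on the 4-weekly rate that occurs: 15.8 to 17.6 points for 80% down to 75%, and 13.2 to 9.9 points for 85% up to 90%. That range is an assumption. Error against the 15-point definition is inflated below 81.8% in the unadjusted calculation. Under the illustrated covariate it is below nominal at 80% and 6.8% at 75%. Comparing a conditional odds ratio with a limit from marginal rates is conservative: it partly offsets the looser margin at low rates and adds to the strictness at high ones.

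**What to change.** Decide on the scale of the definition. From the same logistic model, average the predicted probabilities over all patients under each regimen, and take the standardised (marginal) risk difference, 4-weekly minus 6-weekly, with a 95% interval by delta method or bootstrap. Claim non-inferiority if the upper limit is below 15 points. Keep the adjusted odds ratio as supportive. Amend Protocol 9.4.2 and 9.4.3 and SAP 1.8.2, 1.8.6 and 2.2.2 before any unblinded analysis. The exact-method fall-backs in SAP 1.8.2 and 2.2.2 need a rate-difference counterpart.

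Cost: no extra patients or data, and little programming. It does change the primary decision rule of an open-label trial that has been recruiting since June 2015, so it needs a formal amendment with the approvals listed in Protocol 11.1. Two consequences should be stated openly. The new rule is looser than the present one when the 4-weekly rate exceeds 81.8%: at 90% it tolerates a 6-weekly rate of 75%, an odds ratio of 3.0. It also makes success more likely at the planned rates, with unadjusted power rising from about 76% to 91% with 570 per group.

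If the odds-ratio rule is kept, restate the power as about 75% and say that 2.23 corresponds to 15 points only at a 4-weekly rate of 81.8%.
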